### **Selection of Intervention (EnBrace prenatal supplement)**

The current study will provide evidence regarding the efficacy, tolerability, feasibility and acceptability of a selected non-psychotropic treatment alternative to AD use while women are trying to conceive or during pregnancy. We hypothesize that rates of MDD relapse coinciding with AD discontinuation proximate to pregnancy may be attenuated if there are other effective treatments available to women.

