## **II. SPECIFIC AIMS**

### **a. Specify objectives and hypotheses to be tested**

**Objective:** The overarching goal of this investigation is to assess EnBrace as a treatment for the acute treatment and prevention of depression in women with a history of major depressive disorder who decide to avoid or discontinue their maintenance AD treatment for pregnancy. After completing this protocol, we plan to use the preliminary data for the development of a randomized controlled trial protocol. We will include two groups of women who are interested in minimizing medication exposures while trying to conceive or during pregnancy: 1) women who have histories of depression and are not depressed, and would like to stop antidepressants for pregnancy, 2) women in depressive episodes who are pregnant or trying to conceive (on or off of antidepressant medications).

**Specific Aim 1a:** To evaluate the efficacy of EnBrace when used as maintenance treatment for MDD in a group of women (N=10) who are trying to conceive or are early in pregnancy and who

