## Partners Human Research Committee Detailed Protocol

have decided to stop ADs (Group 1). Relapse rates for women in this context have been demonstrated to be high, with 68% relapse rates in a large multisite NIMH-funded trial.

**Specific Aim 1b:** To evaluate the efficacy of EnBrace when used as an acute treatment for MDD in a group of women (N=10) who are trying to conceive or are early in pregnancy (Group 2). Women will have major depressive episodes in this group, and may receive EnBrace as monotherapy, or as an adjunct to current pharmacotherapy.

*Hypothesis 1a:* We hypothesize that relapse rates will be lower for women who receive EnBrace compared to historical controls. MDD relapse will be determined by the Mini-International Neuropsychiatric Interview (MINI) mood module that will be administered by a study clinician at each visit.

*Hypothesis 1b:* We hypothesize that the majority of women who receive EnBrace will experience a response (50% improvement in depressive symptoms) to EnBrace therapy.

**Specific Aim 2:** To identify biological markers as potential predictors of response to EnBrace.

*Hypothesis 2:* We hypothesize that pre- to post-treatment changes in homocysteine, folate, B12, IL-6 and CRP will be associated with response to EnBrace. We hypothesize specifically that levels of folate and B12 will increase and homocysteine will decrease temporally with treatment and be predictive of prevention of depressive episodes. We hypothesize that treatment will lower IL-6 and CRP levels due to the anti-inflammatory components of EnBrace (i.e., omega-3 fatty acids) and that decreased levels of inflammatory markers may predict lower risk of depressive relapse in participants who enter the study while not on a depressive episode (Group 1), and will predict response to treatment in women who enter the study while in a depressive episode (Group 2).

**Specific Aim 3 (Exploratory):** To identify factors influencing adherence to and tolerability of treatment. This will be achieved by using qualitative methods to explore (a) perceived risks and benefits of treatment; (b) perceived side effect profile; (c) treatment convenience; (d) knowledge of, attitudes towards, and preferences for depression treatment while attempting to conceive or early pregnancy.

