*Hypothesis 3:* We hypothesize that EnBrace will be perceived by patients as 1) an acceptable and attractive treatment with a favorable risk/benefit profile in the context of pregnancy or while trying to conceive, 2) well tolerated, 3) convenient and easy to adhere to, 4) will be a treatment that women who are trying to conceive or who are pregnant find intuitive and preferable to prescription antidepressant medication (or for women on antidepressant treatment in Group 2, who prefer the augmentation with EnBrace rather than an increase in antidepressant dose or augmentation with a prescription psychotropic medication).

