**Schedule of Assessments: Acute Phase (12 weeks)**

Visit #	V1	V2	V3	V4	V5	V6	V7
Week #	0	2	4	6	8	10	12
MINI: full MINI at V1; depression module at follow-ups	X	X	X	X	X	X	X
Demographics, medical & psychiatric history	X						
Labs: genetic sample	X						
Labs: folate, homocysteine, B12, IL-6, CRP	X			X			X
Vital Signs: Height only at V1, weight, blood pressure	X	X	X	X	X	X	X
MADRS	X	X	X	X	X	X	X
CGI-Clinician	X	X	X	X	X	X	X
EPDS	X	X	X	X	X	X	X
QIDS-SR	X	X	X	X	X	X	X
Q-LES-Q-SF	X			X			X

A Qualitative interview will be conducted by study staff after completion of the acute treatment phase in order to obtain feedback on the intervention.

Instrument Descriptions:

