## V. BIOSTATISTICAL ANALYSIS

We will compare the rates of depressive relapse and duration of time out of a depressive episode for Group 1 participants, and compare these data to historical controls that were also assessed prospectively. For Group 2, we will compare depressive response rates (response defined as 50% reduction in depressive symptoms on the MADRS, our primary outcome) to response rates in studies of SSRIs for the treatment of depression.

In addition, we will monitor depressive symptom burden with continuous variables across the treatment study for both groups.

To control for prenatal vitamin (PNV) use, we will supply a standard PNV to each participant to take daily in combination with EnBrace. The Sponsor has offered to supply the PNV, such that each participant will take the same PNV; this will lower the risk of inconsistencies between participants. In the statistical analysis, the data collected in this preliminary study will be compared to historical controls with a history of MDD who discontinued AD maintenance therapy during pregnancy, most of which were taking standard PNVs, but not EnBrace. This reference will allow us to estimate the relative efficacy of EnBrace in relapse prevention of women who discontinue maintenance ADs for pregnancy.

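### Section V gives Group 2 one reference, SSRI-study response rates, without separating women on EnBrace alone from women adding it to an antidepressant, for whom that reference is not matched

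*Combined protocol and SAP*

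**What the plan says.** Specific Aim 1b defines the treatment in Group 2: "Women will have major depressive episodes in this group, and may receive EnBrace as monotherapy, or as an adjunct to current pharmacotherapy". The Objective in Section II likewise admits women on or off antidepressants. Protection Against Risk (Section VI) sets an entry condition for each route: women not on an antidepressant must have declined one, and women already on one must have declined a dose increase or an added drug. No split or cap between the two routes is stated.

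Section V defines response as a 50% reduction on the MADRS, names it the primary outcome, and says Group 2 response rates will be compared "to response rates in studies of SSRIs for the treatment of depression". It names no study, rate, population or time point for that reference and mentions no reporting by background antidepressant. It also plans to follow symptom burden as a continuous measure in both groups. The Exploratory Analyses paragraph covers laboratory tests only.

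Hypothesis 3 does recognise the two uses. It words the preference question separately "for women on antidepressant treatment in Group 2, who prefer the augmentation with EnBrace rather than an increase in antidepressant dose".

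**The concern.** The two kinds of women in Group 2 answer different questions. Women on EnBrace alone bear on its use in place of an antidepressant, which is how Selection of Intervention presents the study: "The current study will provide evidence regarding the efficacy, tolerability, feasibility and acceptability of a selected non-psychotropic treatment alternative to AD use". Women adding EnBrace to a drug bear on augmentation. An SSRI-study rate is at best an external active-treatment benchmark for the first use. It is not a matched reference for the second, because those women continue a drug of their own.

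What is at stake is the use made of the result. The Objective states that "we plan to use the preliminary data for the development of a randomized controlled trial protocol". A trial planner given one Group 2 rate next to an SSRI rate would not know which use it describes, and could credit EnBrace with responses that occurred on a continuing antidepressant.

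**Working it through.** The plan gives no power calculation, reference rate or test for Group 2, so there is no figure of its own to reproduce. The check is first textual, then illustrative.

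**1. What the comparison contrasts**

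| Group 2 woman | Treatment received | Reference in Section V | What the contrast reflects |
|---|---|---|---|
| Not on an antidepressant | EnBrace | SSRI-study rate | EnBrace, natural course and non-specific response, beside an active drug |
| On an antidepressant | Current drug + EnBrace | SSRI-study rate | Drug + EnBrace, natural course and non-specific response, beside an active drug |

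Item 3 of the Drop criteria removes a Group 2 woman who starts an antidepressant or increases its dose. It leaves stable background treatment in place, so the second row remains. No minimum period on a stable dose before entry is stated.

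**2. What one overall rate leaves unshown**

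Inputs: N=10 from Specific Aim 1b; a 5/5 split, which is an assumption. Intervals are exact (Clopper-Pearson): the lower limit is the 0.025 quantile of Beta(x, n-x+1) and the upper limit is the 0.975 quantile of Beta(x+1, n-x).

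- Overall 5/10: 0.187 to 0.813
- 1/5: 0.005 to 0.716
- 4/5: 0.284 to 0.995
- 3/5: 0.147 to 0.947

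An overall 5/10 can be 1/5 alone with 4/5 adjunct, or 4/5 alone with 1/5 adjunct. The overall rate is the same in both. The stratum intervals overlap from 0.284 to 0.716. Fisher's exact two-sided p for 1/5 against 4/5 is 2 × (25 + 1)/252 = 0.21.

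**3. Dependence on the mix**

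With k women on EnBrace alone, the expected overall rate is (k × p_alone + (10 - k) × p_adjunct)/10. Moving from k=2 to k=8 changes it by 0.6 × (p_alone - p_adjunct). All rates below are assumptions.

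- 30% alone, 60% adjunct: (2 × 0.3 + 8 × 0.6)/10 = 54%, falling to (8 × 0.3 + 2 × 0.6)/10 = 36%, a shift of 18 points
- 60% alone, 30% adjunct: 36%, rising to 54%
- 40% in both: 40% at any mix

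For scale, the sampling standard deviation of the overall rate in the first case is √[(2 × 0.21 + 8 × 0.24)/100] = 0.153 at k=2 and √[(8 × 0.21 + 2 × 0.24)/100] = 0.147 at k=8. An 18-point shift is therefore a little more than one standard deviation, but well inside the 62-point width of the exact interval for 6/10 (26-88%). The sign and size depend wholly on the assumed rates.

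**The case against.** The strongest reply is that this is an openly mixed, uncontrolled pilot. Aim 1b and Potential Benefits (Section VII) both name alternative and adjunct use, the data are called preliminary, and a randomized trial is to follow. Hypothesis 1b, that a majority respond, does not rely on SSRI rates. Adjunct women must be in a current episode with a MADRS score of at least 15, so they are still ill on their existing drug, and Drop criteria item 3 limits later antidepressant changes. With strata of about five, a split tests nothing. All of this stands and limits the weight of the point. It does not make an SSRI rate a suitable reference for drug plus EnBrace, and Hypothesis 1b does not separate the two uses either.

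Four stronger readings are tempting, and the documents do not support them:

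- That Section V prescribes a pooled analysis. It never says so; it speaks of response rates and is silent on subgroups. The supportable statement is that it does not require separate reporting.
- That the two ways of reaching 5/10 would lead planners to opposite conclusions. The intervals overlap too much for that.
- That the mix biases the result by a known amount. No response rates or mix are given.
- That Section V treats resemblance to SSRI rates as proof of efficacy. It states only a comparison. That an uncontrolled rate cannot show efficacy is a general limit of a single-arm pilot.

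**Conclusion.** The point holds in a limited form. Section V supplies one external reference for two different uses of EnBrace, and for adjunct women that reference is not matched. A favourable result could be misread as EnBrace performing like an SSRI. The size is a loss of information, not a measurable bias: the 5/10 example assumes a 5/5 split, and the mix calculation rests on assumed rates.

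A reader might infer that splitting the group would isolate the effect of EnBrace. It would not, because neither stratum has a concurrent control. Nor does the point rest on the efficacy wording of Aim 1b, which is a matter of phrasing that Aim 1a shares. The change is worth making because it is cheap and the data are meant to inform a later trial.

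**What to change.** In Section V:

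1. Report Group 2 MADRS response as counts and proportions with exact 95% intervals, overall and by antidepressant use at V1 (yes/no), as description only.
2. Cite SSRI-study rates only as external context for EnBrace-alone women, and not as the comparator for adjunct women. State that without a concurrent control neither stratum isolates the effect of EnBrace.

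The cost is a few sentences and no new visits. The Schedule of Assessments has no row naming antidepressant status, but it can be recorded at V1 under "Demographics, medical & psychiatric history", and Drop criteria item 3 already requires staff to know it. The downside is precision: 3/5 has an interval of 15-95%, so the strata cannot test a difference, and a more uneven split would leave one stratum smaller still.

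Separately, Recruitment Sources (Section III.b) describes Group 2 women as having decided to begin antidepressant monotherapy or to supplement current treatment. Methods of enrollment (Section IV.a) and Protection Against Risk admit women not on an antidepressant only if they do not want to start one. These passages must be reconciled.

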### Exploratory Analyses

We will also explore the collected laboratory tests as potential biomarkers.

## VI. RISKS AND DISCOMFORTS

## Partners Human Research Committee Detailed Protocol

Subject burden for participation includes the time spent participating in study visits. Visits will include a baseline visit (2-3 hours), follow up visits (30 min to one hour each), and three blood draws over the course of the study. The total time burden for subjects is similar to our previous investigations involving very similar populations. Risks of this study include potential psychological distress that may occur during treatment and assessment visits, during which history, current symptoms and life stressors are discussed. Participation in this study does not directly affect risk for recurrence or worsening of depression. To be eligible, subjects must have already made an informed decision regarding antidepressant treatment in the context of pregnancy. Study assessment and treatment visits may increase recognition of symptom worsening and ensure that appropriate treatment is provided. Patients who experience worsening of depressive symptoms will be presented with options for treatment, including antidepressant medications.

According to the NIH National Library of Medicine, adverse reactions to EnBrace that have been reported include: allergic sensitization associated with folic acid; paresthesia, somnolence, nausea, and headaches associated with pyridoxine; and mild transient diarrhea, polycythemia vera, itching, transitory exanthema and the feeling of swelling of the entire body associated with cobalamin. Finally, EnBrace may cause allergic reaction. If patients have any side effects, they will be instructed to report them immediately to the study doctor. If any subject develops an adverse event, the adverse event will be reported to the MGH IRB consistent with Human Research Committee (HRC) guidelines. EnBrace carries no known risks to an embryo, fetus, or breastfeeding infant.

This research study poses the potential risk of subjects consuming higher than recommended doses of B vitamins, iron, and folate when taking EnBrace in combination with a standard prenatal vitamin. The 1.5 milligrams of iron contained in EnBrace is very minimal such that when combined with iron in the typical PNV, there would be little to no risk of exposure to higher than recommended levels of iron. This is also the case for certain B vitamins, which are present in minimal level in EnBrace. Finally, there is potential risk for consumption of higher than recommended doses of folic acid, which can mask vitamin B12 deficiency. To minimize this risk, we will exclude patients with known pernicious anemia or who have had gastric bypass, which may lead to a vulnerability to vitamin B12 deficiency.

As with any clinical research study, there is a potential risk for loss of confidentiality. We will make every effort to keep personal health information confidential.

### Risks of Blood Draws

Phlebotomy can cause pain, bleeding or bruising at the site where the needle enters the vein. Some subjects may feel dizzy or light-headed during a blood draw. There is a very small risk of infection at the site from which we take the blood. A suspected infection would be treated with antibiotics and the subject would be encouraged to follow up with their primary care physician.

### Adequacy of Protection against Risks

Salient safety issues that we address in this section include: 1) ensuring that patients do not feel obligated to enroll in the study, but elect to participate by their own volition 2) caring for patients who may experience a recurrence of their depression during the course of the study 3) maintaining the confidentiality of the study subjects, and 4) ensuring that staff are sensitive to issues of beneficence, justice, race, ethnicity, and gender. The following elements of our proposal are designed to reduce risk for human subjects.

### Recruitment and Informed Consent

## Partners Human Research Committee Detailed Protocol

Subjects will be recruited through the MGH Center for Women's Mental Health and clinician referrals, under the direction of [name] and [name]. At the outset of the proposed investigation, staff psychiatrists and research assistants of the MGH Center for Women's Mental Health will participate in a one-hour meeting with the study PI and co-PI for the purpose of reviewing the aims, design and selection criteria for the proposed investigation.

This clinical and research group sees 900 women annually who are seeking consultation for expert guidance in evaluating the risks and benefits of discontinuing psychotropic medication proximate to pregnancy. Over the last five years, half of these women have suffered from recurrent major depression and have presented on maintenance AD therapy.

We have spent the last decade recruiting a sample of women for perinatal depression (e.g. Prospective Pregnancy Study, n=201, Postpartum Study, n= 129). Under a separate MGH IRB approved protocol we have permission for ongoing dynamic contact with these patients as they proceed through their reproductive life cycles. Through this system, we have recruited participants for two large scale research studies involving pregnancy.

Also, for an NIMH R-21 funded study to assess depressive relapse risk in women undergoing infertility treatment, we successfully recruited 49 participants. We also recruited N=12 women for a CBT study in pregnancy, designed to utilize CBT to reduce the risk of depressive relapse in women trying to conceive and discontinuing ADs.

The Clinical Research Department has a seamless relationship with the Clinical Center. At the Clinical Center, psychiatrists see over 600 women a year for consults regarding treatment recommendations for psychotropic medication during pregnancy.

Every woman who comes to either the Research Program to participate in a clinical trial or for a consult with one of the psychiatrists in our program has the opportunity to fill out a form allowing us to enter her information into our tracking system. This is also complemented by our internet resource center ([www.womensmentalhealth.org](http://www.womensmentalhealth.org)) as well as a seasonal e-newsletter with nearly 4,000 subscribers.

These critical recruitment tools generate a constant flow of patients that may be eligible and interested in participating in the current study. If a potential Group 1 patient indicates that she is undecided on whether she wants to discontinue her antidepressant treatment or elects to stay on antidepressant treatment, she will not be informed about the current study.

Informed consent will be obtained by one of the research psychiatrists from patients at the start of the baseline visit, prior to conducting any study assessments or procedures. The PI or another member of the study team (MD or PhD-level clinician) who is trained in all study assessment procedures will review the consent form with all patients. Subjects in this study must be capable of understanding the nature of this study as well as the discomforts and potential benefits. These will be explained in full by the HRC-approved research staff. All subjects will then be asked to read, understand, and sign the informed consent prior to participation.

### **Protection Against Risk**

As discussed above, in order to (1) prevent patients from feeling obligated to participate in the study, subjects eligible for Group 1 will only be enrolled if they decide to discontinue AD treatment. Subjects eligible for Group 2 will only be included if they have decided not to accept treatment with an antidepressant medication (if not currently on an antidepressant) or opt not to increase the dose or add an adjunctive antidepressant medication (if presenting on an antidepressant). The risks and benefits of

## Partners Human Research Committee Detailed Protocol

discontinuing maintenance AD treatment will be described to the patient in detail. Additionally, the research clinician will inform the patient that they can choose, at any point, to reinitiate AD treatment.

For (2) prompt identification of patients who experience a depressive recurrence or worsening of acute depression during the study, it is likely that over the course of the investigation some women may have significant psychiatric symptoms requiring acute intervention and/or evaluation and referral. The investigators have the clinical expertise and resources available to provide acute evaluations and, if needed, referral. The Acute Psychiatry Service of the MGH is staffed and available 24 hours/day to handle psychiatric emergencies. Because subjects are assessed for mood symptoms at each study assessment visit, the likelihood that symptom worsening will be identified in a timely manner is increased.

As in all clinical research studies, it will be critical to (3) maintain the confidentiality of the women with psychiatric illnesses and/or treatment. Data collected in the study will be used for research purposes only. All members of the research team will treat all data with strict confidentiality. All members of the research team, prior to working on a research protocol, are required to complete a designated course in the ethics and regulations governing research with human subjects. Documentation of completion of this course will be required for all study personnel at the beginning of the investigation. Subject confidentiality will be assured by use of identification numbers on pre-coded data collection sheets. Only one master log with identifying information linking the patient name and the identification number will be maintained and kept in a secure location separate from the remainder of the study data. Signed informed consent forms will be kept in a locked room for documentation purposes. Any paper data obtained during the investigation, which includes interview, symptom rating scale, and lab result forms, will be kept in a separate secure filing cabinet with access limited to the research team. After recruitment and analysis of data are complete (at the end of the funding period), all subjects' identifying information will be destroyed and will not be included as part of long-term storage of data sets. No data will be reported on an individual basis; all findings will be presented in aggregate.

Additional steps will be taken to protect confidentiality of genetic data as outlined:

1. All study staff are trained to make confidentiality of genetic data a priority.
2. No genetic research data (or any other data related to the study) will be entered into the medical record.
3. The results of the genetic analyses will only be shared with participants who elect to receive them through secure email, postal mail, or in person at study visits using an approved letter. This information will not be shared with their family members or unauthorized third parties. All questions regarding genetic results will be deferred to participants' treating providers.
4. Genetic data are encoded using coded identifiers. These codes, rather than personal identifiers, are used in any analytic datasets. The code key linking coded identifiers to personal identifiers are kept in an access-restricted, password protected electronic file and are not shared with the genetics laboratories.
5. Samples and genetic data stored in the laboratory will be identified only by the code numbers and laboratory personnel will not have access to personal identifiers.
6. The most serious risk would be identification of individuals in the publicly shared database. To prevent this, computerized data files provided to other investigators will not include any of the HIPPA-defined personal identifiers.

In order to assure that the (4) subject's personal contribution to this research study is acknowledged, all study staff will receive training in human subject research, which includes emphasis on issues of confidentiality, respect, beneficence, justice, race, ethnicity and gender.

